Week = from quit day (0). Ax = Assessment. F/U = follow-up. R = Randomization. Tx = *Visit by can be by phone. **Additional baseline measures (see C.6). ***Body adiposity scan

Medication. Formulation. Bupropion XL 150mg, and placebo tablets matching in appearance (Rejuvination Labs, San Diego, CA) will be used. **Regimen.** The selected regimen was based on medication guidelines¹⁸¹ and evidence that a 4-week extended run-in prior to quit day produces superior outcomes relative to the standard 1-week run-in,⁷⁰ All dosing is once per day per XL formulation guidelines.¹⁸² BUP-450 involves a 17-day up-titration (1 x 150 mg tablet for 3 days followed by 2 x 150 mg tablet for 14 days), 10-day pre-quit run-in (3 x 150 mg tablets), 8-week post-quit treatment period (3 x 150 mg tablets), and 1-week down-titration (2 x 150 mg tablet). The BUP-300 regimen is identical except that pre-quit run-in and 8-week post-quit treatment period involves 1 x placebo + 2 x 150mg to match number of tables taken across conditions and differentiate dose. **Clinical monitoring/safety:** In addition to eligibility screen, participants will meet with the physician at: (a) treatment outset to review the medication, managing and/or reporting side effects, pregnancy contraindications, and rationale for taking the medication for ≥ 4

weeks prior to quitting; and (b) end of treatment to review treatment, collect labs, and discuss down-titration. All participants will be given a 24-hour phone number and physician office hours will be available as needed. Vital signs, weight, and side effects, including suicidal ideation, will be monitored at each study visit. In the event that significant medical problems are encountered, the blind will be broken and appropriate medical treatment will be provided.

Cessation counseling. All participants will be offered bibliotherapy (NCI- Clearing the Air)¹⁸³ and receive seven 10-20 min sessions based on the USDHHS clinical practice guidelines. Trained counselors (blind to treatment), supervised by [name], a licensed clinical psychologist, will provide the counseling, which focuses on enhancing social support, problem solving, coping skills, and check-ins on medication adherence. Three pre-quit visits focus on establishing the quit-date and preparation. Four post-quits focus on reinforcing abstinence (or encouraging the resumption of cessation) and continued support. There is a final check-in at the end of the medication treatment period. Some visits will be offered via phone (Table).

C.6 Measures (see Table for the assessment schedule).

Screening and baseline measures. (1) Medical history interview for bupropion contraindications; (2) Physical exam; (3) Blood and urine for liver/kidney function, drug screen, and pregnancy; (4) EKG to rule out unstable cardiovascular disease; (5) Clinical Institute Withdrawal Assessment for Alcohol¹⁸⁴ to rule out alcohol-related seizure risk (score ≥ 10); (6) Structured Clinical Interview for DSM-5 (SCID) modules for diagnostic rule outs and other Axis-I disorders for descriptive purposes (PTSD, MDD, Dysthymia, Social Anxiety, ADHD)¹⁸⁵; (7) Tobacco Product Use History Questionnaire (e.g., age of onset, cig/day, use of other tobacco products, etc.); (8) FTND;¹⁷⁹ (8) Ten-Item Drug Abuse Screening Test (DAST-10)²⁰³, with no record made regarding specific names of drugs used, and (9) Premenstrual Symptoms Impact Survey¹⁸⁶ and date of last menstruation, given evidence that these factors influence quit outcomes¹⁸⁷ will be used in supplemental sex-specific analyses (C.7).

Core assessments (all in-treatment visits). To aid counselors' intervention, collect cessation milestone outcomes (C.7), and to monitor safety, we will administer: (a) smoking timeline follow-back to track smoking,¹⁸⁸ (b) 8-item Minnesota Nicotine Withdrawal Scale,¹⁸⁹ (c) Systematic Assessment for Treatment Emergent Events¹⁹⁰ and open ended reports coded by Medical Dictionary for Regulatory Activities Version 14.0.

Supplemental assessments: mediators. We will use a multi-method assessment strategy to tap multiple facets of reward processing and behavior that have shown sensitivity to the main effect of nicotine abstinence and differences in abstinence effects by anhedonia level:⁹ (1) Self-report Tripartite Pleasure Inventory, which instructs participants to rate the extent of pleasure, frequency of engagement and desire for (irrespective of engagement) 12 typically-enjoyable activities during the past week,¹⁹¹ (2) The Emotional Interference Gender Identification Task,¹⁹² which examines social reward processing by measuring extent to which the pictures of actors displaying happy (relative to neutral or angry) facial expressions on a computer capture one's attention and consequently distract and slow the speed of identifying the actor's gender by pressing a corresponding key (10 min); (3) A reward learning task,¹⁹³ which measures the extent to which respondents modulate their behavior in response to reward. Participants will be asked determine length of visual stimulus presented on the screen by pressing a key (long or short; the actual difference is difficult to judge). One response will be differentially reward at \$.05 per trial relative to the other. The extent to which choices become biased towards the more rewarded choice reflects the degree of reward learning (10 min; (4) The 5-item Brief Questionnaire of Smoking Urges (QSU)¹⁹⁴ Factor 1 scale of desire to smoke for pleasure; (5) The 10-item Positive and Negative Affect Schedule (PANAS)¹⁹⁵ positive affect scale. To examine discriminant validity of effects, we use the 5-item QSU Factor 2 measure of desire to smoke for negative affect relief, and the PANAS negative affect scale.

Outcome assessments (Baseline, 4-wk, 8-wk, 16-wk, 26-wk). Primary outcome: Point prevalence abstinence (PPA) self-report of no smoking or use of any other tobacco products (including e-cigarettes) in past 7-days (not even a puff) verified by salivary cotinine ≤ 10 ng/ml is our primary outcome. Secondary outcomes: (a) Smoking cessation milestones derived from Smoking Timeline Follow Back interview (i.e., achieving ≥ 24 hr abstinence, days to lapse, days from lapse to relapse; C.7), (b) The 29-item Inventory of Depressive and Anxious Symptomatology¹⁹⁶ Social Anxiety, General Depression, Traumatic Intrusions subscales; (c) 18-item Adult Self-Report Scale for ADHD¹⁹⁷ adapted for past-week symptom assessment; (d) SHAPS anhedonia scale,¹⁸⁰ (e) objective body weight via a medical-grade scale; (d) adiposity via bioimpedance monitor (InBody520, GE Healthcare)—a non-invasive 2-min scan that analyzes body electrolytes to yield fat, muscle, and water composition estimates, which we will use to generate percent body fat outcomes. In addition to self-reports of medication adherence, detectable bupropion, >5 ng/mL in urine¹⁹⁸ during study visits will be used as a supplemental marker. Though participants will be told to avoid use of other quit treatments, e-cigarettes, or tobacco/nicotine

products during the trial, these will still be assessed via self-report and participants who report transitioning to e-cigarettes will be analyzed as an exploratory intermediate outcome.

C.7 Analytic Plan

Preliminary Analyses. Distributions will be examined to determine the need for normalizing transformations. Using ANOVA or X^2 test, we will examine if groups differ at pretreatment on relevant variables (despite randomization) to inform possible inclusion in analyses.

Primary Aim 1: Smoking Outcome. 7-Day biochemically-verified PPA (missing coded as smoking) at 4- 8- 16- and 26-week post-quit follow-up will be evaluated using individual latent growth curve models (LGCM) for longitudinal binary outcomes including planned covariates (FTND, sex, SHAPS anhedonia score, BMI), the main effects of medication (BUP-450 vs. BUP-300), and the effect of time. Non-linear effects of time will be explored using nested likelihood ratio tests prior to evaluating hypotheses. Treatment by time interactions will be examined to characterize medication effects before and after treatment termination. To understand at what stage of the cessation process the treatments exert their effects, we will also analyze cessation milestone outcomes of attaining abstinence (yes vs. no abstinent for >24hr in the first 2 weeks post-quit), days to lapse (i.e., first puff), and days from lapse to relapse (i.e., first puff until the onset of 7 consecutive days of smoking) using logistic and cox regression. Sensitivity analyses of treatment effects will examine medication adherence and counseling visit attendance as moderator of treatment effects and we will re-analyze primary models in the subset of fully-adherent participants. Additional comparisons of side effects between the conditions will be conducted to verify tolerability of BUP-450.

Primary Aim 2: Mediation. Aim 2 will examine slopes from individual piece-wise LGCMs (or raw difference scores when only 2 timepoints available) to model changes in reward processing (see C.6) prior to quit day, the jump from pre to 1-week post-quit, and post-quit changes. A latent variable framework using Mplus 7.4 will allow estimates of treatments on individual growth in mediators (path 'a') to be modeled jointly with effects of growth in likelihood of abstinence (path 'b') using models that limit bias in estimates and provide accurate evaluation of mediation using bias corrected effect estimation and product of coefficients procedures. We will attempt to create a composite that amalgamates all reward processing mediators using principal component analysis (PCA), or if a strong component is not detected, test each raw variable individually. We will model time to lapse first and other smoking outcomes secondarily with and without smoking as a time-vary covariate. Additional multiple mediator models adding all 3 growth pieces simultaneously and including the discriminant constructs (negative affect, urge to smoke to alleviate negative affect) will be test the specificity of effects.

Secondary Aims: Aim 3 will examine medication effects on anhedonia (SHAPS) and related psychopathology (i.e., depressive, social anxiety, ADHD, PTSD symptoms) and body weight and body fat percentage trajectories using individual growth models (intercept and slope) of assessments at visits during treatment. Moderation of the differential effect of treatment (Aim 4) will be assessed with interaction terms of treatment condition and corresponding moderators (SHAPS, depressive, social anxiety, ADHD, PTSD symptoms) in successive models as described above in LGCM.

Supplemental analyses of the biological variable of sex and other characteristics (age, ethnicity/race). Using the strategies above, we will examine if sex, ethnicity/race, and FTND moderate treatment effects on primary and secondary outcomes. We will report sex-stratified analyses and test, amongst women, whether days since menstruation at the onset of treatment and quit day moderates outcome using several classification methods (follicular vs. luteal; early follicular vs. late follicular vs. mid luteal vs. other).

Missing data. Prior to testing primary hypotheses we will conduct exploratory analyses to determine if baseline characteristics (e.g. sociodemographics, smoking) predict patterns of missingness. Any marginally significant ($p < .10$) predictors of missingness will be included as covariates in LGCM models above and used with multiple imputation methods for evaluating obtained model estimates.¹⁹⁹ Maximum likelihood estimation of multilevel models with Mplus has the advantage of using all available data. Mplus also incorporates special facilities for maximum likelihood estimation with data missing either completely at random, or data missing at random (missing data can be a function of observed covariates) with continuous, categorical, or count outcomes and facilitates analyses using multiply imputed data.

C.8 Sample Size Considerations

We determined power/ sample size using an empirical power analysis.²⁰⁰ Estimated PPA rates for BUP-450 (45%, 38%, 30%, 30%), BUP-300 (30%, 25%, 20%, 20%) at the 4-, 8-, 16- and 26-week assessments were based on previous literature, including Cochrane Review summaries of BUP-300 effects on quitting, known

relapse curves in anhedonic smokers, BUP-450 vs. BUP-300 vs. PLA effects on weight loss and mental health.^{22,97,162} We generated 1,000 multivariate normal random samples of correlated binary outcomes using covariance estimates from prior trial data (range 0.55-0.25)³ and analyzed the datasets using LGCM focusing on the proportion of significant ($p < 0.05$) values for each pair-wise contrast (Aim 1). The percentage of datasets with significant effects for each hypothesis (i.e., $>80\%$ of $ps < .05$) provided a simulation-based estimate of power. Using this technique, we found that enrolling a sample size of 375 (BUP-450: $N < 150$, BUP-300 $N < 150$) conservatively would have power >0.83 to detect main effects when testing our primary hypothesis, allowing for 20% attrition among those enrolled. Parallel simulations were conducted using LGCM to assess power for growth trajectories in continuously scaled mediators assuming an effect of treatment dose response on reward processing ($ds > 0.3$), and reward processing on outcome ($ds > 0.17$) based on the prior literature.^{131,140,201,202} We also found support for power >0.81 with average effects of 0.31 ($sd = 0.11$) with $N = 375$. Additional simulations for secondary mental health and body/weight adiposity outcomes based effects in prior literature ($ds > 0.3$)^{22,97,162} yielded adequate power ($> .80$). Missing individuals will be presumed to have continued smoking. All analyses will use an intent-to-treat approach.

REFERENCES

4. [name] AM, Zvolensky MJ. Anxiety, depression, and cigarette smoking: A transdiagnostic vulnerability framework to understanding emotion-smoking comorbidity. *Psychological bulletin*. 2015;141(1):176.
5. Gorwood P. Neurobiological mechanisms of anhedonia. *Dialogues Clin Neurosci*. 2008;10(3):291-299.

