Extended pre-quit run-in treatment regimen. The standard bupropion regimen involving a one week pre-quit run-in prior to the quit date may be insufficient for maximizing clinical outcomes because: (1) bupropion and its dopaminergic agonist metabolite hydroxybupropion do not reach steady-state concentrations until 5–8 days of treatment;¹⁰⁷ (2) more frequent smoking under bupropion-induced attenuation of nicotine reward may facilitate extinction of smoking behavior and improve bupropion's efficacy;⁷⁰ and (3) bupropion-induced attenuation of anhedonia and some of bupropion's other antidepressant effects often take 3-4 weeks to emerge.⁸¹ The proposed trial will apply a novel 4-week extended pre-quit run-in treatment regimen that may be more sensitive to detecting bupropion's efficacy than the standard 1-week run-in, as evidenced by a prior trial of BUP-300 demonstrating superior quit outcomes with a 4-week (vs. 1-week) pre-quit run-in.⁷⁰

Cessation milestones. PPA amalgamates several distinct milestones of the cessation process that may be underpinned by distinct mechanisms: (1) starting the quit attempt and establishing >24 abstinence vs. avoiding quitting altogether; (2) maintaining continuous abstinence vs. lapsing; and (3) amongst lapsers, recovering abstinence vs. relapse back to regular smoking patterns. In our prior work, BUP-300 improved establishment of abstinence, prevented lapse, but did not shorten time from lapse to relapse among lapsers,¹⁰⁸ and post-quit anhedonia predicted worse outcomes for all three milestones.⁵⁷ Supplemental analyses will test the effect of BUP-450 on milestones to elucidate how this novel treatment exerts its effects in anhedonic smokers (C.7).

Measurement of body fat composition outcomes. For the small subset of cessation trials that do report weight-related outcomes, body weight is the predominant index, which is an unreliable measure of adiposity due to regular fluctuations in water retention and muscle changes that may take place during cessation. In an innovative application of obesity research to smoking, we will use a bioimpedance monitor to accurately index body fat and muscle composition via electrical conductance in a non-invasive 2-min scan. As such, we anticipate greater sensitivity and clinical significance for detect for detecting a pro-metabolic effect of BUP-450.

[figure not shown]
C. APPROACH

C.1 Progress Report for R01-DA26831, Project Period: 8/15/09 – 11/30/13

[figure not shown]

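### The lapse-to-relapse Cox model compares only participants who lapsed, a subset that treatment may change, so it cannot by itself show at which stage BUP-450 acts

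*Combined protocol and SAP*

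**What the plan says.** Section C.7 (Primary Aim 1) lists three cessation milestones, to be analysed by logistic or Cox regression: attaining more than 24 hours of abstinence, days to lapse, and "days from lapse to relapse (i.e., first puff until the onset of 7 consecutive days of smoking". Their stated purpose is "To understand at what stage of the cessation process the treatments exert their effects".

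Section B (Cessation milestones) describes the third one as "amongst lapsers, recovering abstinence vs. relapse back to regular smoking patterns". The same paragraph reports from the team's earlier work that BUP-300 "prevented lapse, but did not shorten time from lapse to relapse among lapsers", and that "post-quit anhedonia predicted worse outcomes for all three milestones".

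Section C.6 lists the milestones as secondary outcomes taken from the timeline follow-back interview, and section B calls their analysis supplemental. FTND, sex, SHAPS score and BMI are named as covariates for the growth model of point prevalence abstinence (PPA). None are named for the Cox models. The plan has no relapse endpoint in all randomized participants, no multi-state or joint model, no sensitivity analysis for this milestone, and no caveat on its interpretation. Section C.8 adds a general sentence: "All analyses will use an intent-to-treat approach".

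**The concern.** The clock for this model starts at the first puff, so only people who have lapsed can enter it. Lapsing is a post-randomization event that the trial hopes to influence. Suppose BUP-450 keeps the less vulnerable smokers from lapsing. Those who still lapse on BUP-450 are then, on average, more vulnerable than those who lapse on BUP-300, and they would relapse faster even if the drug did nothing after lapse. The lapsers-only HR mixes that selection with any real post-lapse effect.

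Section B points to both ingredients. It reports that bupropion (at 300 mg) changed who lapses, and that a common factor, anhedonia, drives every milestone. At stake is the mechanistic conclusion: a drug that only prevents lapse could be described as inactive or harmful once a lapse has occurred.

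**Working it through.** **No figure to reproduce.** The documents give no lapse rate, event count, HR or power for this milestone. The check below therefore rests on assumptions, and only the size of the bias depends on their values.

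**Inputs from the documents.** 150 participants per arm (Specific Aims); 26 weeks of follow-up, or 182 days (C.6); p < 0.05 (C.8), taken as two-sided.

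**Assumed.** Exponential times to lapse and from lapse to relapse. A shared frailty u multiplies both hazards. It is gamma distributed with mean 1 and variance v. Mean lapse-to-relapse time is 30 days at u = 1. BUP-450 acts on lapse only, so the true post-lapse HR is 1.00. Everyone starts abstinent on quit day. The main case has 80% lapsing on BUP-300 and 70% on BUP-450.

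**Step 1: how different are the lapsers?** With q the proportion still lapse-free at 182 days, mean frailty among lapsers is (1 − q^(1+v)) / (1 − q). At v = 1:
- BUP-450: (1 − 0.30²)/0.70 = 0.91/0.70 = 1.30
- BUP-300: (1 − 0.20²)/0.80 = 0.96/0.80 = 1.20

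The ratio is 1.30/1.20 = 1.08. An imbalance of that size therefore arises from selection alone.

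**Step 2: what the Cox model returns.** The lapse HR that gives 70% against 80% is (0.30^(−v) − 1)/(0.20^(−v) − 1). At v = 1 this is 2.333/4 = 0.58. At v = 0 it is ln 0.30/ln 0.20 = 0.75. HRs come from 200,000 simulated people per arm, and rejection rates from 2,000 trials of 150 per arm (about 185 to 205 relapse events each).

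| v | Lapse HR | Mean frailty of lapsers, 450 / 300 | HR among lapsers (truth 1.00) | Significant against BUP-450 (nominal 2.5%) | HR, quit day to relapse, all randomized |
|---|---|---|---|---|---|
| 0 | 0.75 | 1.00 / 1.00 | 1.00 | 2.5% | 0.76 |
| 0.5 | 0.67 | 1.19 / 1.14 | 1.05 | 4.6% | 0.76 |
| 1 | 0.58 | 1.30 / 1.20 | 1.09 | 8.8% | 0.77 |
| 2 | 0.42 | 1.39 / 1.24 | 1.16 | 17.4% | 0.80 |

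**Step 3: other assumptions.**
- Lapse 75% against 62%: HR among lapsers 1.05, 1.10, 1.20 at v = 0.5, 1, 2.
- Lapse 90% against 82%: 1.05, 1.10, 1.16.
- Log-normal frailty, lapse HR 0.6, mean times of 30 days: 1.04, 1.06, 1.08 at log-variance 0.5, 1, 2, moving by about 0.02 between runs. The bias is smaller because 90% to 97% of the BUP-300 arm lapses, which leaves little room for selection. Two-sided type I error was 6.3% at variance 1 and 9.1% at variance 2.
- Over all the gamma scenarios, including v = 0, the all-randomized HR ran from 0.70 to 0.86.

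**Step 4: does adjusting for time to lapse help?** It does not. In the log-normal set-up the HR among lapsers moved from 1.03, 1.05, 1.07 to 1.08, 1.12, 1.17. In the gamma set-up it reached 1.06, 1.12, 1.34. With log-normal frailty, two-sided type I error at N = 300 rose from about 7–11% to about 13–28%. Of two people who lapse on the same day, the one on the arm that prevents lapse is frailer on average, so conditioning on lapse day sharpens the imbalance.

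**The case against.** **The bias is conditional and modest.** It needs both a lapse effect of BUP-450 over BUP-300 and a shared cause of lapse and relapse. The lapse result that section B reports concerns BUP-300, so a further effect of the higher dose is only hypothesized. Without shared frailty the bias is zero, and the larger values come from variance 2. This stands and limits the weight of the point.

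**The stakes are low.** The milestones are secondary and supplemental, and no primary inference or power figure depends on them. This also stands.

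**The added endpoint does not answer the stage question.** Time from quit day to relapse merges the milestones that section B sets out to separate, and PPA in all randomized participants already gives a total effect. This stands in part. The endpoint does not locate a stage, but it gives relapse, as the plan defines it, a comparison of the randomized arms, which PPA at four visits does not. A multi-state or shared-frailty model would come closer to the stage question, at the price of assumptions about frailty.

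**Intent to treat.** A reader might infer that a lapsers-only model contradicts the sentence in C.8. The documents do not support that. The sentence can mean analysis by assigned arm, with missing participants counted as smoking, as C.7 and C.8 specify. A milestone openly defined among lapsers does not breach that reading. The fair criticism is narrower: the comparison is not a randomized one.

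**Conclusion.** The point holds as a modest, conditional weakness in a secondary analysis. The model compares a subset that treatment may itself change, so it cannot on its own support a conclusion about the stage at which BUP-450 acts.

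If BUP-450 reduces lapse and lapse and relapse share causes, the HR is biased against BUP-450. With no true post-lapse effect it is about 1.03 to 1.10 at frailty variance 0.5 to 1, and about 1.07 to 1.20 at variance 2. Lapse rates, frailty distribution and event times are all assumed.

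A reader might infer that the analysis will show BUP-450 to be harmful after lapse. The figures do not support that: in the main gamma case a significant adverse result appears in 4.6% to 17.4% of simulated trials with shared frailty, and at the nominal 2.5% without it.

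**What to change.** 1. Add a Cox model of time from quit day to relapse (onset of seven consecutive smoking days) in all randomized participants. Count those who never reach 24 hours of abstinence as relapsed at quit day, and name this as the randomized relapse comparison. State how these day-zero events are coded, since some software drops zero times.
2. Keep the lapsers-only model but label it descriptive. Adjust it for baseline FTND, SHAPS, sex and BMI only, and not for time to lapse. Baseline adjustment removes only the part of the shared risk that those variables explain.
3. State in C.7 that no causal conclusion about stage will be drawn from the lapsers-only HR.

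The cost is a few lines of analysis-plan text and one extra model on timeline follow-back data already planned, with no new visits or participants. The downside is that the all-randomized endpoint gives a total effect and does not isolate the lapse-to-relapse stage.

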- 2. To test whether treatment-related enhancement of reward processing is a mechanism of action of high dose bupropion.** Hyp 2. The effects of BUP-450 vs. BUP-300 cessation outcomes will be mediated by reward processing, such that dose will predict greater improvements in reward processing, which will in turn be associated with greater odds of abstinence.

Secondary Aims

- 3. To test the effects of high dose bupropion on secondary outcomes of:** (a) anhedonia and related psychopathology (i.e., depressive, social anxiety, ADHD, PTSD symptoms), and (b) change in body weight and percent body fat composition.
- 4. To examine if baseline anhedonia level and related psychopathology (depressive, social anxiety, ADHD, PTSD symptoms) moderate the efficacy of high dose bupropion on cessation outcome.**

If successful, this research may identify a novel, highly-disseminable, cost-effective, and efficacious cessation treatment for an at-risk population, with wide-spanning implications toward offsetting three of the nation's top causes of morbidity and mortality—smoking, mental illness, and health problems due to excessive weight.

A. SIGNIFICANCE

A.1 Importance of Increasing Cessation Treatment Outcomes for Smokers Psychiatric Symptoms

While the overall population-level rate of smoking has significantly declined in recent years, smoking among those with psychiatric symptoms and conditions has remained stable,¹⁸ with SWPS accounting for a mounting proportion of the U.S. tobacco-related disease burden each year.¹ A key source of the tobacco-related health disparities facing SWPS is their disproportionately low quit rates.¹ Hence, improving smoking cessation among SPWS is vital for reducing tobacco-related disparities and counteracting the public health burden of smoking.

A.2 Current Status of Cessation Treatment Development Research for SWPS

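### Aim 2's fallback tests each raw mediator in up to three growth pieces with no lead test and no multiplicity rule; if mediators predict lapse but dose does not move them, a false mediation finding could approach one in two

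*Combined protocol and SAP*

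**What the plan says.** The Specific Aims list mediation as the second of two primary aims, with one hypothesis: "The effects of BUP-450 vs. BUP-300 cessation outcomes will be mediated by reward processing".

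C.6 says of the mediators: "We will use a multi-method assessment strategy to tap multiple facets of reward processing and behavior". It then numbers five: a pleasure inventory with three kinds of rating, an emotional-interference task, a reward-learning task, the pleasure factor of the smoking-urge questionnaire, and positive affect.

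C.7 (Primary Aim 2) models change in each mediator in three pieces: "prior to quit day, the jump from pre to 1-week post-quit, and post-quit changes". It attempts one composite by principal component analysis (PCA) but, "if a strong component is not detected, test each raw variable individually". The test is described only as "bias corrected effect estimation and product of coefficients procedures". On outcomes: "We will model time to lapse first and other smoking outcomes secondarily with and without smoking as a time-vary covariate". Further models are described as "Additional multiple mediator models adding all 3 growth pieces simultaneously", together with the negative-affect constructs as a specificity check.

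Neither C.7 nor C.8 defines a strong component, names a lead mediator or lead piece, sets a significance level for Aim 2, or mentions a multiplicity adjustment.

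**The concern.** The data decide how many tests address one primary hypothesis. With a composite there are three, one per growth piece. Without one there are about 15, and the plan does not say how many must be significant, or at what level, for Hyp 2 to count as supported. One nominally significant result among them could be reported as the mechanism of action that section B sets out to identify.

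The fallback is a realistic contingency. The composite would have to combine two computer tasks with self-reports chosen to cover different facets, and the plan itself allows for a weak component.

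**Working it through.** **Inputs.** N=300 randomized 1:1 (Specific Aims). Five mediators (C.6), three pieces (C.7). Mediator effects of d=0.3 for dose on mediator (path a) and 0.17 for mediator on outcome (path b), both from C.8. Two-sided 0.05 per test is an assumption: C.8 uses 0.05 in its power simulation and C.7 states no level for Aim 2.

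**The plan's own figure.** C.8 gives power above 0.81 for the mediator models at N=375, and 300/(1−0.20)=375.
- Path a alone: Φ(0.30×√(375/4)−1.96) = 0.828, close to 0.81.
- Path b, reading 0.17 as a standardized coefficient: Φ(0.17×√375−1.96) = 0.909.
- Both paths: 0.828×0.909 = 0.75. At N=300: 0.738×0.838 = 0.62.

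So the stated figure matches one path of one test. C.8 gives no familywise error rate to reproduce.

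**Upper reference.** For k independent 5% tests, 1−0.95^k is 0.143 (k=3), 0.401 (10), 0.537 (15) and 0.659 (21).

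**Why this overstates some cases.** An indirect effect needs both paths. If dose has no effect (a=0), the joint-significance error per test is about 0.05 × power for b. At N=300:
- b=0 everywhere: 0.05×0.05 = 0.0025 per test; over 15, 1−0.9975^15 = 0.04.
- b=0.17 everywhere: 0.05×0.838 = 0.0419 per test; over 15, 1−0.9581^15 = 0.47. For 3, 10 and 21 tests: 0.12, 0.35 and 0.59.
- b=0.17 in one piece only: 1−0.9581^5×0.9975^10 = 0.21.

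**Simulation**, N=300, 15 tests, a linear outcome standing in for time to lapse (1,000 trials, 1,000 resamples). Ranges run from correlated mediators (0.2 between measures, 0.4 between pieces) to independent ones:

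| True state | Joint significance | Normal-theory product | Bias-corrected bootstrap |
|---|---|---|---|
| a=0, b=0 | 0.04 | <0.01 | 0.09 |
| a=0, b=0.085 (independent only) | 0.22 | 0.02 | 0.37 |
| a=0, b=0.17 | 0.43–0.48 | 0.15–0.16 | 0.60–0.68 |
| a=0, b=0.25 (independent only) | 0.54 | 0.34 | 0.70 |
| a=0, b=0.35 (correlated only) | 0.50 | 0.42 | 0.59 |
| a=0.3, b=0 (correlated only) | 0.38 | 0.09 | 0.58 |

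A separate simulation with correlation 0.3 gave 0.45–0.50 (joint) and 0.16–0.29 (normal-theory product) when every mediator predicts outcome. With one predictive piece it gave 0.21 and 0.06; with neither path real, 0.04 or less. If only two of the five mediators are directly predictive, joint significance gives 0.31 (b=0.17) to 0.38 (b=0.25).

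**With adjustment.** Holm over the 15 tests kept the joint-significance error at or below 0.05 in every state of the correlation-0.3 simulation. Bias-corrected bootstrap limits at the Bonferroni level (0.05/15 = 0.0033) still gave 0.05–0.11 when one path was real at 0.17 or more. That range is rough, because 1,000 resamples are few for such tails.

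**The case against.** The strongest reply is that a reader might infer an unconditional even chance of a false claim, and the documents do not support that. The figure needs the fallback to be triggered, dose to move no mediator, and every mediator in every piece to predict lapse. C.8 assumes that reward processing affects outcome, not that 15 separate b paths are real. This stands, and the risk has to be given as a range by scenario. The half-chance end is still plausible: the plan expects path b to be real, and C.2 reports earlier trials in which falling positive affect raised relapse risk and urge mediated the standard dose's efficacy. The open question is path a.

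A reader might also infer that bias-corrected bootstrap intervals are specified. C.7 speaks of bias-corrected estimation and names neither intervals nor a bootstrap, so the 60–70% figure is conditional. The finding does not need it.

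The number of tests is uncertain. The supplemental row of the C.5 schedule shows no clear week-1 mark, though the table may be broken in extraction; two estimable pieces would make 10 tests. Twenty-one rests on scoring the pleasure ratings separately, which C.6 does not state. A contrast of one test against 21 would also be wrong, because the composite route already has three.

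Finally, the plan does have structure: composite first, time to lapse first, and multiple-mediator models with discriminant constructs. It never says that one significant raw variable confirms Hyp 2. That is fair, but ordering the outcomes does not limit the mediators or pieces, and leaving the success rule open is the gap itself. Aim 1's efficacy test does not depend on any of this.

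**Conclusion.** The concern holds as a gap in the specification of a primary aim. As written, C.7 lets the number of tests of Hyp 2 go from three to about 15 on an undefined criterion, with no lead test and no error control.

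If dose moves no mediator and all mediators predict lapse, the false-finding risk over 15 tests could reach about 45–50% by joint significance, about 15–30% with a normal-theory product test (higher if b is well above 0.17), and 60–70% with bias-corrected bootstrap limits. With one predictive piece it is about 6–21%; with neither path real, below 10%. These figures assume N=300, 5% per test, and a linear stand-in for time to lapse. Models with and without the smoking covariate, and the secondary outcomes, would add tests and are not counted.

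**What to change.** In C.7, Primary Aim 2:

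1. State a numeric PCA retention criterion before unblinding, and orient component scores so that higher means better reward processing. The smoking-urge score must be reversed, since A.6 expects helpful treatment to lower urge and raise positive mood.
2. If the composite is retained, name one growth piece and time to lapse as the single confirmatory test of Hyp 2. The composite alone is not enough, because three unadjusted pieces still carry up to 0.143.
3. If the fallback is used, declare Hyp 2 supported only on Holm-adjusted p-values across all mediator-by-piece tests.
4. Label the other pieces (under the composite route), other outcomes and covariate variants as supportive.
5. State the test that supplies the p-values and, if bootstrap limits are intended, their type.

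The change is wording only. Its cost is power for any single raw mediator. At N=300 with a=0.3 and b=0.17, one test at 0.05 has power of about 0.62. At Holm's first step (0.0033, z=2.935) it is Φ(2.598−2.935)×Φ(2.944−2.935) = 0.368×0.504, about 0.19. Later Holm steps are less strict if several mediators are real. The single composite test avoids this penalty.
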